2.3. Study Protocol

The study protocol is depicted in Figure 1. Interested individuals completed an online prescreening questionnaire prior to a phone interview with research personnel in order to assess for initial eligibility. For individuals who met initial inclusion criteria, an in-person screening visit was held at the UAB Center for Clinical and Translational Science Clinical Research Unit (CRU). All participants provided written informed consent at the in-person screening. Baseline study questionnaires were administered on a tablet device, and vital signs and venous blood samples were collected by CRU staff to assess for exclusionary laboratory values. Participants were also provided with computer tablet devices to take home with them in order to complete once daily symptom reports during the entire study period. A one-month baseline symptom reporting period began immediately following the in-person screening visit. Participants were required to complete at least 80% of daily symptom reports during this period to remain eligible for the study.

[figure not shown]

Figure 1. Study protocol. Each participant completed testing of up to three botanicals. For each botanical, there was a placebo condition, followed by lower-dose botanical and higher-dose botanical conditions. The period of time between visits was 30 ± 3 days. Some participants reenrolled in the study after completion, receiving up to a maximum of six botanicals.

Pseudo-randomization was then performed so that participants were assigned to receive up to three out of the nine botanical compounds, as shown in Figure 1. Pseudo-randomization was done in such a way to prevent drug interactions that contraindicated the use of the botanical in a given participant. There were no contraindications for the use of luteolin. Because blood glucose may be lowered by resveratrol [37] and fisetin [38], individuals taking medications for diabetes, or with evidence of prediabetes or diabetes, were excluded from taking these agents.

Additionally, individuals with clotting disorders, hypotension, or those taking anticoagulants or

Additionally, individuals with clotting disorders, hypotension, or those taking anticoagulants or antihypertensive medications were excluded from taking resveratrol, due to its effects on blood pressure [39,40]. Prophylactic use of 81 mg aspirin daily was permitted.

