2.3. Study Protocol

Individuals were screened via an online questionnaire and phone interview, followed by an in-person screening conducted at UAB's Clinical Research Unit (CRU). Informed consent was obtained at the in-person visit, and blood samples were collected for further screening. As the screening involved blood tests, individuals provided informed consent before being determined eligible for participation. Therefore, several individuals who provided consent were not eligible to participate in the study. Consented individuals received a tablet device for completing daily symptom reports each evening for the duration of their study participation.

Before beginning capsules, all participants completed a baseline period of 30 days. This period served as the baseline for all botanicals taken by the participant. Participants then were pseudo-randomized to receive up to three of the nine study compounds, as seen in **Figure 1**. A pseudo-randomized procedure was used to avoid contraindications with the botanicals. Randomization was conducted by a pharmacist. The pharmacist in charge of blinding and randomization was not otherwise involved in the study. The research personnel were blinded to the botanicals assigned to each participant. For each botanical, participants completed 30 days of placebo capsules, 30 days of lower-dose botanical, and 30 days of higher-dose botanical. Participants were blinded to all aspects of the study (the protocol and botanicals assigned). Research personnel were blinded to the botanicals assigned, though they were aware that placebo occurred first, followed by lower-dose and higher-dose treatment.

[figure not shown]

Figure 1. Study event flow. Participants took three of the tested compounds in the following order: placebo, lower-dose botanical, and higher-dose botanical.

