Throughout their involvement with the study, participants returned to the CRU every month. At these visits, participants would obtain a new supply of study capsules. Blood samples were also obtained at visits 4, 7, and 10 to conduct safety tests. Standard clinical renal and hepatic panels were performed. Participants first took the lower dosage and then the higher dosage of the botanical so that any renal or hepatic issues could be detected before the participant took the larger dosage. Participants received compensation during each visit. The participants received a total of \$1500 for attending all 11 of the study visits and completing the protocol. Participants who successfully completed all three botanical assignments were allowed to enroll in the study a second time, where they would be assigned new botanicals.

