2.6. Statistical Analyses

All analyses were conducted in SPSS version 24 (IBM Corp., Armonk, NY, USA). For each botanical, a linear mixed model (LMM) was created to test changes in the primary outcome. LMMs were used to accommodate the repeated outcome assessments in each condition, nested in each participant. Subject ID was the repeated-measures nesting variable, the repeated-measures index was the day in the study, and the repeated measures covariance type was compound symmetry. The predictor was study condition, which could take four values (baseline, placebo, lower-dose, and higher dose botanical). The last 14 days of each condition were included in the models. The final 14 days of the baseline condition at the beginning of participation were used as the baseline for all tested botanicals. Post hoc tests were conducted using least-squares differences. A p < 0.05 was used for all tests. The same statistical approach was used to test the secondary outcomes of pain and fatigue. Nine total models are presented in this report (three botanicals tested for the outcomes of GWI severity, pain and fatigue).

If a participant did not complete the protocol, any valid data were still used in statistical tests. However, data imputation of missing values was not used, and participants were not included if they never took the assigned botanical. Therefore, we did not use a complete intent-to-treat method for analysis.

The three trials were powered to detect within-person fixed effects for study condition (baseline, placebo, lower dosage and higher dosage). Detection of a medium effect size (Cohen's d = 0.5) was targeted at a threshold of p < 0.05. With 56 repeated outcome assessments per participant, and a repeated measures correlation of 0.5, it would require 10 individuals to achieve 0.99 power for the main effect test.

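### For second and third botanicals the condition test uses a baseline about 4 to 9 months old, so it can turn significant without any botanical effect

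*Combined protocol and SAP*

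**What the plan says.** The reuse rule is written in the reishi/nettle/epimedium report. Section 2.3 places the baseline ahead of all treatment, "Before beginning capsules, all participants completed a baseline period of 30 days", and adds: "This period served as the baseline for all botanicals taken by the participant". Section 2.6 of that report carries the rule into the analysis: "The final 14 days of the baseline condition at the beginning of participation were used as the baseline for all tested botanicals". Study condition, with the levels baseline, placebo, lower dose and higher dose, is the only predictor named. Day in the study is the repeated-measures index under compound symmetry, not a covariate.

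The sequence is set out in section 2.3 of the same report: "Participants then were pseudo-randomized to receive up to three of the nine study compounds", and "For each botanical, participants completed 30 days of placebo capsules, 30 days of lower-dose botanical, and 30 days of higher-dose botanical". No new baseline between blocks is described. On re-enrolment the report says "Participants who successfully completed all three botanical assignments were allowed to enroll in the study a second time". The Figure 1 legend of the resveratrol/luteolin/fisetin report adds: "Some participants reenrolled in the study after completion, receiving up to a maximum of six botanicals". No report says when a second enrolment began or whether it opened with a new baseline month.

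The curcumin/boswellia/maritime pine and resveratrol/luteolin/fisetin reports use the same four-level factor and describe one baseline month, but do not state which baseline serves later botanicals.

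**The concern.** The untreated month adjoins only the first block. For a later botanical, one or two complete 90-day blocks of placebo and other agents lie between the baseline level and the three levels it is tested against. Season, natural course, change in how a man uses the scale, and earlier agents can all move ratings over that gap, and the gap differs between takers of the same botanical according to its place in their sequence. The curcumin/boswellia/maritime pine report itself describes the baseline month as a habituation period, so some movement away from it is plausible.

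Baseline is inside the test that was powered, so a displaced baseline can make that test significant when placebo, lower dose and higher dose are identical. The least-squares-difference contrasts against baseline carry the same problem.

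Reuse is a second issue. One man's unusually bad baseline fortnight appears as improvement in all his botanicals together, so agreement between botanicals is weaker evidence than it looks.

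**Working it through.** **Inputs.** From the reishi/nettle/epimedium report, sections 2.3 and 2.6: 30-day baseline, three 30-day periods per botanical, last 14 days of each condition analysed, up to three botanicals per enrolment, 56 assessments, correlation 0.5, 10 men, d = 0.5, power 0.99. From section 2.7 of the other two reports: power 0.42 at d = 0.25. Period tolerance of 3 days either way: section 2.3 of the curcumin/boswellia/maritime pine report.

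**1. The plan's power figure.** Treat the assessments as one within-person factor in a single group, with f = d/2, λ = f² × N × m / (1 − ρ), and degrees of freedom m − 1 and (N − 1)(m − 1).
- d = 0.5, N = 10, m = 56: λ = 0.0625 × 10 × 56 / 0.5 = 70; df 55 and 495; power 0.997 (stated 0.99).
- d = 0.25: λ = 0.015625 × 10 × 56 / 0.5 = 17.5; power 0.417 (stated 0.42).

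The formula reproduces both figures. Since 56 = 4 × 14, the baseline days are counted in the powered test.

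**2. Age of the baseline.** From the midpoint of the baseline window to the midpoint of period j (1 placebo, 2 lower, 3 higher) of the k-th botanical, the gap is 90 × (k − 1) + 30 × j days.

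| Botanical | Placebo | Lower dose | Higher dose |
|---|---|---|---|
| 1st | 30 | 60 | 90 |
| 2nd | 120 | 150 | 180 |
| 3rd | 210 | 240 | 270 |

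This is 4 to 6 months for the second botanical and 7 to 9 for the third. With every period at 27 or at 33 days, the ranges are 108–198 and 189–297 days. Only if re-enrolment followed at once with no new baseline do the fourth to sixth botanicals run from 300 to 540 days, about 10 to 18 months.

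**3. Effect on the four-level test.** Set placebo = lower = higher and shift only the baseline, by δ SDs of a daily rating on average over the takers. Under compound symmetry with ρ = 0.5 the residual variance is 0.5. The squared deviations of the four means sum to 0.75δ², so λ = 10 × 14 × 0.75δ² / 0.5 = 210δ², with df 3 and 560 − 10 − 3 = 547.
- δ = 0.10: λ = 2.1, rejection 19.9%.
- δ = 0.20: λ = 8.4, rejection 67.4%.
- δ = 0.25: λ = 13.1, rejection 87.2%.

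A single dose-versus-baseline contrast has standard error √(2 × 0.5 / 140) = 0.085 and rejects 21.9% of the time at 0.10 SD and 65.8% at 0.20 SD. A test of the three within-block conditions stays at 5%. The values of δ are illustrations.

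**4. Shared baseline.** With equal, otherwise independent period errors, two dose-minus-baseline contrasts in the same men correlate at Var(baseline) / [Var(baseline) + Var(dose)] = 0.5. If only a fraction p of each botanical's takers is shared (equal group sizes), the correlation is 0.5p. If each man took three of nine botanicals uniformly (assumed), p = 2/8 = 0.25 and the correlation is 0.125. At full overlap, simulation gives a 19% chance that a false positive in one botanical is joined by a same-direction false positive in a second, against 2.5% if independent. For three botanicals, the chance of at least one false positive falls slightly (12.4% against 14.3%), while two or more becomes likelier (2.2% against 0.7%).

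**5. Power with three levels.** m = 3 × 14 = 42, N = 10. At d = 0.5, λ = 0.0625 × 10 × 42 / 0.5 = 52.5, df 41 and 369, power 0.985. At d = 0.25, λ = 13.125, power 0.349.

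**The case against.** The rule is openly stated, and it uses the only period free of every agent. Each botanical also has its own placebo month just before dosing, so the dose-minus-placebo difference in means does not depend on the baseline's age. Only the last 14 days of the habituation month are used, which limits early rating drift, and no drift rate is documented. Within any one model a man's baseline enters once, so nothing is double-counted there. All of this stands, and it narrows the point to the four-level test and the baseline contrasts.

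It could also be said that a term for block number would repair the model without dropping baseline. It would not do so as a main effect: in one botanical's model a man has a single block number, so the term is constant within him and cannot absorb a shift between his baseline and his treatment windows.

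Four stronger readings are tempting and not supported:
- A reader might infer that the baseline is up to 18 months old and feeds six models per outcome. That requires re-enrolment without a new baseline. The section 2.6 wording about the start of participation leans that way, but the curcumin/boswellia/maritime pine report speaks of re-enrolling into the protocol, which opens with a baseline month. The documents do not settle it.
- A reader might infer that 6 months is the minimum age for later botanicals. That holds only for the higher-dose window of the second botanical; its placebo window is 4 months away.
- A reader might infer that the baseline itself is contaminated by other agents. It precedes all capsules; it is the later blocks that follow other agents.
- A reader might take 0.5 as the correlation between any two botanicals. It needs the same men in both models, and the documents give no count of shared participants.

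**Conclusion.** The point holds for the reishi/nettle/epimedium report as written. For second and third botanicals, the four-level main-effect test and every baseline contrast compare treatment windows with a baseline about 4 to 9 months older, across exposure to other agents, with no term to separate these influences from the botanical. The test is sensitive to this: about 20% false rejection at a 0.10 SD shift and 67% at 0.20 SD. Those rates rest on 10 men, 14 days per condition, compound symmetry with correlation 0.5, and an assumed shift. The size of any real shift is unknown.

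The same baseline values enter up to three models per outcome, and up to six only if re-enrolment took no new baseline. Baseline contrasts are therefore correlated between botanicals to the extent that the same men took them.

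The comparison of a dose with its own block's placebo mean is not biased by the age of the baseline. For the other two reports the reuse rule is likely, given the shared design, but unstated.

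**What to change.** - Base the inferential test for each botanical on placebo, lower dose and higher dose of the same block (three levels, 42 days), and report baseline descriptively. Do not count a significant four-level test or baseline contrast as evidence of a botanical effect.
- Restate the power basis as 42 assessments: 0.985 at d = 0.5 and 0.35 at d = 0.25 with 10 men, on the plan's own formula.
- State whether re-enrolled men gave a new baseline, and which baseline their later botanicals used.
- State whether the other two reports applied the same reuse rule.
- The four-level model can be kept as a sensitivity analysis, labelled with the baseline's age by place in the sequence.

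Cost: one change to the model specification and its wording, with no new data. Stated power falls by about one percentage point at d = 0.5 and about seven at d = 0.25 (0.417 to 0.349). There is no longer a formal baseline contrast. The reference becomes a placebo month that, in later blocks, comes straight after another agent's higher dose with no stated washout. That limitation remains and should be reported alongside the three-level result.

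### Excluding participants who never took the assigned botanical makes entry to each analysis depend on getting through the placebo month, which may bias the placebo contrasts if stopping was related to symptoms

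*Combined protocol and SAP*

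**What the plan says.** The rule stands in section 2.6 (Statistical Analyses) of the reishi, stinging nettle and epimedium report. Non-completers are in general retained: "If a participant did not complete the protocol, any valid data were still used in statistical tests". Two qualifications follow: "data imputation of missing values was not used", and "participants were not included if they never took the assigned botanical". The report draws the consequence itself: "Therefore, we did not use a complete intent-to-treat method for analysis".

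Section 2.3 of the same report fixes the order of conditions: "For each botanical, participants completed 30 days of placebo capsules, 30 days of lower-dose botanical, and 30 days of higher-dose botanical". Section 2.3 of the other two reports gives the same order. On the data used, section 2.6 states "The last 14 days of each condition were included in the models" and "The final 14 days of the baseline condition at the beginning of participation were used as the baseline for all tested botanicals".

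Section 2.7 of the curcumin/boswellia/maritime pine report and section 2.7 of the resveratrol/luteolin/fisetin report do not say how non-completers were handled. None of the three reports' methods gives the number, timing or reasons of withdrawals, or a sensitivity analysis for this rule.

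**The concern.** A rule that requires a first active dose is usually harmless when the comparator is a separate arm. Here the comparator is an earlier month in the same person, so the rule acts on the comparator. A man who stops during or just after placebo has not taken the botanical and leaves that botanical's models altogether. A man who stops one month later stays in. Entry is decided after placebo symptoms have been experienced.

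At stake are the placebo-versus-baseline contrast and the dose-versus-placebo contrasts. If men who felt worse on placebo tended to leave, the retained placebo mean is too low: placebo looks better than it was and each dose looks worse against it. If men who felt well left, both signs reverse. The linear mixed model accepts partial records without imputation, and already does so for those who stop on active capsules.

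**Working it through.** **1. The plan's own figure.** The stated power is 0.99 for 10 participants, 56 assessments, correlation 0.5 and d = 0.5. For a within-subject F test with f = d/2 = 0.25: λ = f²·N·m/(1 − ρ) = 0.0625 × 10 × 56/0.5 = 70, with 55 and 495 degrees of freedom, so power is 0.997. For d = 0.25, λ = 17.5 and power is 0.417 (stated: 0.42 in the other two reports). Both reproduce. If 10 were the number assigned and the rule removed one or two, power at d = 0.5 would be 0.991 or 0.978. The question is bias, not power.

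**2. Who is removed.**

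| Stops | Has taken the botanical? | That botanical's models |
|---|---|---|
| During or just after placebo | No | All rows dropped |
| In the lower-dose month | Yes | Valid data kept |
| In the higher-dose month | Yes | Valid data kept |

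**3. When this causes bias.** Assume no true effect, and write each month's mean as a stable personal level plus a deviation for that month. Contrasts are within-person, so the level cancels. Random stopping, or stopping that depends only on the stable level, gives zero bias. Two cases do not:
- Stopping driven by the change from baseline to placebo: baseline and placebo deviations are selected equally and oppositely. Dose minus placebo is biased by −½ times the bias in placebo minus baseline, and dose minus baseline by +½ times it.
- Stopping driven by the placebo-month level: dose minus placebo is biased by the full opposite amount, and dose minus baseline not at all.

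**4. Size on the VAS.** None of these inputs is in the documents; all are assumptions: between-person SD 15, month-to-month SD 8, daily SD 15 with 14 reports, and a leave decision that is half signal and half noise in variance (correlation r = 0.707 with its driver).

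Variance of a monthly deviation: 64 + 225/14 = 80.07. SD of the change: √(2 × 80.07) = 12.65. With a proportion p leaving, the bias in placebo minus baseline is −r × k × 12.65, where k = φ(z)/(1 − p), φ is the standard normal density and z cuts off a tail of p.

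| Leaving (assumed) | k | Placebo − baseline | Higher dose − placebo |
|---|---|---|---|
| 10% | 0.195 | −1.7 | +0.9 |
| 20% | 0.350 | −3.1 | +1.6 |
| 30% | 0.497 | −4.4 | +2.2 |

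Simulation with 200,000 participants per scenario agrees to within 0.1 point. For month SD 5 to 12 and 20% leaving, the bias in dose minus placebo is +1.1 to +2.2. If the placebo level drives leaving, it is r × k × (deviation variance)/(SD of level). At month SD 8 that is 0.707 × 0.350 × 80.07/17.47 = +1.1; over month SD 5 to 12 it is +0.6 to +2.0.

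A separate simulation in units of total SD (10% to 30% leaving, other variances and selection strengths) gave 0 to 0.25 SD in magnitude on placebo minus baseline and 0 to 0.12 SD on higher dose minus placebo.

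**5. Keeping the rows.** With placebo-month leavers retained in the compound-symmetry model, change-driven leaving leaves about zero bias. Level-driven leaving does not, because daily compound symmetry ignores month-to-month variation within a person. At 20% leaving and month SD 5, 8 and 12, simulated bias in higher dose minus placebo falls from +0.62, +1.18 and +2.01 points to +0.18, +0.46 and +0.83, a reduction of about 60% to 70%. These runs gave every leaver 14 placebo reports.

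**The case against.** The strongest reply is that this is a declared choice. The report says outright that the analysis is not complete intent-to-treat, and contrasts are within-person, so only symptom-related stopping in the placebo month matters. That stands as far as it goes, but the disclosure neither explains discarding valid placebo reports nor addresses what this does to the placebo contrasts.

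Any bias is also small beside the noise. On the SDs assumed above, the standard error of higher dose minus placebo with 10 participants is √(2 × 80.07/10) = 4.0 points, so a bias of 1.6 is 0.4 of a standard error. The targeted d = 0.5 is 0.5 × √(225 + 64 + 225) = 11.3 points. This limits the practical weight. However, with about 10 per botanical, one or two exclusions already make 10% to 20%.

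Some entry rule is needed. One baseline serves every botanical a man is assigned, so without a rule someone who quits in his first cycle could lend baseline rows to botanicals whose cycle he never began. That is right: the issue is where entry is set, not whether to have it.

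Two stronger readings are tempting. A reader might infer that the placebo comparator was in fact selected on its own outcome and that the reported contrasts are biased. The documents do not show this: it needs placebo-month withdrawals to have occurred and to have depended on that month's symptoms, and neither is reported. A reader might also infer that the other six botanicals were analysed under a different rule. Silence there shows incomplete reporting only.

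**Conclusion.** The asymmetry is real. It follows from the stated exclusion together with the fixed placebo-first order, on a literal reading of never having taken the botanical. Whether it biased any contrast cannot be told from the documents. The range runs from zero to a few VAS points: under the assumptions shown with 10% to 30% leaving, up to about 4.4 points on placebo minus baseline and 2.2 on higher dose minus placebo at month SD 8, with either sign possible. Those dropout rates, SDs and selection strengths are illustrations, not estimates for this trial. The power statement is essentially unaffected. The change is worth making because a better population can be formed from data already held. If nobody stopped in a placebo month, reporting that closes the point.

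**What to change.** For each of the nine botanicals:
- Include every participant who was dispensed that botanical's placebo kit, with all valid baseline, placebo and dose data, whether or not active capsules were started. Leave out participants whose cycle for that botanical never began.
- Define the analysis window for a cut-short placebo month, for example the last available reports up to 14 days. A condition tied to the last 14 days of a full month would drop early leavers again.
- Show the current population as a sensitivity analysis.
- Report withdrawals by month and reason.
- State whether the exclusion was also applied to the six botanicals in the other two reports.

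Cost: revised SAP wording, a re-run of the models and a withdrawal table; no new data. A few included participants will have no active-dose data. As shown above, the change reduces but does not fully remove bias when leaving depends on the placebo-month level.
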